8.4.4. Liver Histology

A paired biopsy sub-study was recommended by Regulatory Authorities, to further assess clinical outcomes in terms of histological progression to cirrhosis and is described in Protocol Addendum 2. While biopsies were collected, no paired data exists; no analysis will be run.

8.5. Interim Analyses

A single interim analysis was conducted when 63% of the total events were reached. The interim analysis was conducted and reviewed by the Data Monitoring Committee (DMC) according to the Interim Analysis Statistical Analysis Plan. No further interim analysis for superiority or futility is planned for this study. This is a deviation from the protocol. Further details are described in [Section 14.1](#).

8.6. Multiple Comparisons/Multiplicity

An interim analysis was conducted after 80 events were observed. A group sequential design using the O'Brien-Fleming type alpha-spending function ([Lan 1983](#), [Reboussin 2000](#)) was used to control the overall two-sided 0.05 significance level that is at an information fraction of 0.63 of the total of 127 events, corresponding to an alpha spend of 0.009. The primary analysis will be conducted at 2-sided 0.041 significance level. No interim analysis will be performed based on the updated endpoints and methodology. The primary endpoint analysis for European Medicines Agency (EMA) filing will be conducted at 2-sided 0.041 significance level.

For the final analysis, the hypothesis testing of key secondary analyses will compare placebo and OCA (the key secondary endpoints are stated in [Section 8.2](#)), provided that the primary efficacy endpoint comparison is statistically significant in favor of OCA. If the primary comparison is not statistically significant then comparison of the key secondary endpoints will be considered as supportive or supplemental. If the primary comparison is statistically significant, the key secondary endpoints will be tested hierarchically in the order described in [Section 8.2](#) at a 2-sided 0.041 significance level. All other secondary endpoints will be tested at nominal 0.041 alpha level.

8.7. Subgroup Analyses of Efficacy

The primary and all key secondary efficacy endpoints ([Section 8.2](#)), liver biochemistry ([Section 8.3.2](#)), and prognostic endpoints and markers of inflammation endpoints ([Section 8.3.3](#)) will be analyzed for subject subgroups based on the ITT population. Sensitivity analyses will not be run for subgroup analyses. Subgroups will be assessed at Baseline. Baseline subgroups of interest are as follows:

- Baseline disease stage:
 - On-label per United States Prescribing Information (USPI). The on-label subgroup includes ITT subjects who had not experienced clinically evidence portal hypertension (CSPH) or decompensation at baseline.
 - A subject is defined to have CSPH at baseline if they had any of the following: a previous history of portal hypertension includes procedures for TIPS, sclerotherapy, ligation, HVPG measurement >10 mmHG, paracentesis, thoracentesis (due to hepatic hydrothorax); previous history or baseline observation of preferred terms for presence of collateral circulations secondary to CSPH, GI bleeding due to varices or portal hypertension, gastroesophageal varices without bleeding and portal hypertensive gastropathy, ascites, hepatopulmonary syndrome,

hepatorenal syndrome, portopulmonary hypertension, hepatic encephalopathy; platelets $<150 \times 10^9/L$ with splenomegaly and/or with transient elastography >15 kPa.

- A subject is defined to have decompensation at baseline if they had any of the following: a Child-Pugh score of B or C; previous history or baseline observation of preferred terms for gastric variceal or esophageal variceal bleeding, ascites, hepatic hydrothorax, spontaneous bacterial peritonitis, hepatic encephalopathy, hepatorenal / hepatopulmonary / portopulmonary syndrome, prior TIPPS or other peritoneovenous shunt.
 - Compensated, non-cirrhosis or cirrhosis. The pre-decompensation subgroup includes ITT subjects who had not experienced decompensation at baseline.
 - Decompensated. The decompensated subgroup includes ITT subjects who had experienced decompensation at baseline.
 - Contraindicated per USPI. The contraindicated subgroup includes ITT subjects who had experienced CSPH and/or decompensation at baseline.

The primary efficacy endpoint and key secondary endpoints will also be assessed for the following baseline subgroups of interest if there are a sufficient number of subjects in each group (eg, >5 subjects per group):

- Sex: male, female
- Age categories (at time of informed consent): <65 years, ≥ 65 years
- Age categories at PBC Diagnosis (at time of informed consent): <50 years, ≥ 50 years
- Race: white, non-white
- Ethnicity: Hispanic, non-Hispanic
- Baseline bilirubin level: $>ULN$, $\leq ULN$
- Baseline use of UDCA: Yes, No

The primary efficacy endpoint will also be assessed across the spectrum of PBC disease stage as defined by Rotterdam criteria ([Kuiper 2009](#))

- Early (normal albumin and normal bilirubin)
- Moderate (abnormal albumin or abnormal bilirubin)
- Advanced (abnormal albumin and abnormal bilirubin)

If a strong correlation between biochemistry and clinical outcomes using the ITT population is observed, the biochemical improvement in the subpopulations (baseline disease stage, Rotterdam disease severity, and monotherapy) will be further assessed.

9. SAFETY ANALYSES

Safety analyses include exposure to study treatment, treatment-emergent adverse events (TEAEs), clinical laboratory parameters, electrocardiograms (ECGs), vital signs, and any abnormal findings observed during physical examinations after study enrollment and through discontinuation of study treatment or within 30 days after the discontinuation of study treatment. Data after a patient begins commercial OCALIVA will be excluded. Safety analyses will be performed using the Safety Population including by treatment groups. No inferential comparison of safety endpoints will be performed, unless otherwise specified.

9.1. Exposure to Study Treatment

The extent of exposure will be summarized using descriptive statistics. Duration of exposure (days) to IP will be calculated as follows:

$$\text{Exposure to investigational product} = \text{Date of last IP dose} - \text{Date of first IP dose} + 1 \\ - \text{Total duration of temporary IP discontinuation.}$$

The duration of each incidence of temporary investigational product discontinuation will be calculated as follows:

$$\text{Duration of temporary discontinuation of investigational product} = \text{Date of restart of IP} - \text{Date of temporary discontinuation of IP} + 1.$$

The total duration of temporary IP discontinuation is the sum duration of temporary discontinuation of IP over each incidence of discontinuation.

Total subject exposure to IP will be calculated by adding the doses taken by a subject during the study and will be summarized using descriptive statistics.

A summary of subjects who had an increase in dose and who had a decrease in dose at least once during the study will be provided in terms of frequency count (n) and percentages (%).

Dose and frequency will be modified for subjects with cirrhosis (including subjects progressing to cirrhosis during the study) and classified as CP-B or CP-C. Therefore, any adjustments, interruptions, discontinuation, and any rechallenge of IP will be summarized.

Subject's overall compliance (%) with IP will be calculated as follows:

$$100 \times (\text{number of tablets consumed during study} / \text{number of tablets expected to be consumed during study})$$

where

- number of tablets expected to be consumed during study = number of dispensed tablets during the study

and

- number of tablets consumed during study = number of tablets dispensed – number of tablets returned.

Subject compliance with IP will be summarized by treatment group using descriptive statistics. Percent compliance will be summarized separately for subjects who completed the study and

those who withdrew early so as to distinguish between those subjects who were compliant throughout the entirety of the study versus those who were compliant until they withdrew from the study.

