9.2.4. TEAE Analyses

The number of events and counts and percentages of unique subjects experiencing a TEAE and TEAEs by PTs and SOC in the following categories will be presented for the Safety Population:

- TEAEs

- TEAEs by highest severity (mild, moderate, severe): At each level of subject summarization, a subject is classified according to the highest severity if the subject reported 1 or more events. AEs with missing severity will be considered severe for this summary.
- Serious AEs
- Adverse events of special interest
- AESIs by highest severity (mild, moderate, severe): At each level of subject summarization, a subject is classified according to the highest severity if the subject reported 1 or more events. AEs with missing severity will be considered severe for this summary.
- TEAEs leading to study treatment discontinuation: This is a subset of the AEs where action taken with study treatment is checked as “Drug withdrawn” or where “Subject Discontinued from Study” is checked.
- TEAEs leading to study treatment interruption: This is a subset of the AEs where action taken with study treatment is checked as “Drug interrupted”.
- TEAEs leading to study treatment dose reduction: This is a subset of the AEs where action taken with study treatment is checked as “Dose reduced”.
- Deaths: This is a subset of the AEs where “Fatal” is checked.
- Subject incidence of TEAEs by MedDRA SOC, PT, and closest relationship to investigational product (Related/Not Related). Related AEs are those with relationships reported by the Investigator as “Definite,” “Probable,” or “Possible,” and unrelated AEs are those with relationships reported as “Unlikely” or “Not Related.” At each level of subject summarization, a subject is classified according to the closest relationship if the subject reported 1 or more events. AEs with a missing relationship will be considered related for this summary.

Summaries will be sorted in order of decreasing frequency in the treatment arm. Summaries will also be presented by MedDRA SOC and PT, sorted in alphabetic order of SOC and then in order of decreasing frequency in the treatment arm.

Exposure-adjusted incidence of TEAEs will also be provided by SOC and PT. Each individual subject year on study will be derived as the last known date during the study minus the first dose date plus 1 divided by 365.25 days/year.

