Percentages based on frequency counts will be based on available data, and denominators will generally exclude missing values, unless otherwise stated. For frequency counts of categorical variables, categories whose counts are zero will be displayed for the sake of completeness. For example, if none of the subjects discontinued due to “lost to follow-up,” this reason will be included in the table with a count of 0. Percentages based on frequency counts will be presented as a whole number (no decimal places), and values less than 1% will be presented as “<1%.” Values less than 100% but that round up from 99.5% to 100% will be presented as “>99%.”

Quantitative laboratory tests containing less than (<) and greater than (>) symbols are test results that are below and above quantifiable limits, respectively. In order to retain these values for analysis purpose, the following imputations will be done within the analysis datasets:

For laboratory test results that are below the quantifiable limit:

Imputed laboratory results = (numeric portion of the result) x 0.9.

For laboratory test results that are above the quantifiable limit:

Imputed laboratory results = (numeric portion of the result) x 1.1.

For the purpose of tabulations, the unscheduled post-baseline values generally will be excluded from summary tables, but will be included in data listings. Unscheduled visits will be considered for analyses of shift from baseline to worst value (low-normal-high).

Standard Calculations

Variables requiring calculation will be derived using the following formulas:

- First dose date is defined as the day of first dose of IP received after randomization
- Last dose date is defined as day of the last dose of IP
- Time to event – The time to an event will be calculated in days as the date of the first occurrence of the event minus the date of first investigational product administration plus 1
- Days – A duration expressed in days between one date (*date1*) and another later date (*date2*) will be calculated using the following formulas:

duration in days = $date2 - date1 + 1$, where $date1 \geq$ first dose date

duration in days = $date2 - date1$, where $date1 <$ first dose date

- Months – A duration expressed in months is calculated as the number of days divided by 365.25/12 (approximately 30.4)
- Years – A duration expressed in years between one date (*date1*) and another date (*date2*) is calculated using the following formulas:

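### The interruption formula in SAP Section 9.1 counts the restart day as off drug, so descriptive exposure duration is understated by 1 to 2 days per interruption under daily dosing

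*SAP*

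**What the plan says.** Section 9.1 of the SAP builds the duration of exposure in two steps.

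- The gross span is the last dose date minus "Date of first IP dose} + 1". From this it subtracts the "Total duration of temporary IP discontinuation".
- Each interruption is the "Date of restart of IP" minus the "Date of temporary discontinuation of IP} + 1". These are then added up: "The total duration of temporary IP discontinuation is the sum duration of temporary discontinuation of IP over each incidence of discontinuation".

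The section does not say whether the date of temporary discontinuation is the last day a dose was taken or the first day one was missed. Appendix A (Standard Calculations) gives a general rule for intervals that start on or after the first dose, "duration in days = $date2 - date1 + 1", which is probably where the added day comes from.

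Two related measures are defined differently. In Section 9.1, "Total subject exposure to IP will be calculated by adding the doses taken by a subject during the study". In Section 9.2.4, subject-years for exposure-adjusted event rates are "the last known date during the study minus the first dose date plus 1 divided by 365.25 days/year".

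**The concern.** Adding 1 to a difference of dates is right when both end dates belong to the state being counted. That holds for the gross span, because subjects take drug on the first and the last dose date. It does not hold for an interruption, because the interval ends on the day drug is taken again. The formula therefore books at least one dosed day as off drug. If the discontinuation date is the last dosed day, it books two.

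The error always runs the same way and occurs once per interruption, so it accumulates instead of averaging out. What is at stake is the accuracy of the exposure-duration table and of its repeat by baseline disease stage (Section 9.8). Because the stop date is undefined, two programmers could also follow the same text and get different answers, both too low.

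**Working it through.** The SAP gives a formula here and no figure, so there is no stated result to reproduce. The check is to count dosed days directly and compare.

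**Inputs.** The two formulas are from Section 9.1. Daily dosing applies to most subjects, and once- or twice-weekly dosing to Child-Pugh B or C (Section 3). Follow-up of about 6 years is from Section 3, taken as 6 × 365.25 ≈ 2192 days. The gap length of 7 days is an assumption, used only to gauge size.

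**Daily dosing, one gap.** Doses on Days 1–10 and 21–30, none on Days 11–20. True time off is 10 days, true exposure 20 days, gross span 30 − 1 + 1 = 30.

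| Stop date means | SAP interruption | SAP exposure | Error in exposure |
|---|---|---|---|
| First missed day (Day 11) | 21 − 11 + 1 = 11 | 30 − 11 = 19 | −1 day |
| Last dosed day (Day 10) | 21 − 10 + 1 = 12 | 30 − 12 = 18 | −2 days |

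The error does not depend on gap length. In 20,000 randomly generated single gaps it was −1 or −2 days every time, according to the reading of the stop date.

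**Several gaps, daily dosing.** With k interruptions the loss is k to 2k days. For three 7-day gaps (21 days truly off):

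| Span | True exposure | SAP exposure | Relative error |
|---|---|---|---|
| 2192 days | 2171 | 2168 or 2165 | −3/2171 = −0.14% or −6/2171 = −0.28% |
| 365 days | 344 | 341 or 338 | −3/344 = −0.87% or −6/344 = −1.74% |

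**Once-weekly dosing.** Doses on Days 1 and 15, with the Day 8 dose missed. From the first missed dose to restart is 15 − 8 = 7 days. The SAP formula gives 15 − 8 + 1 = 8 days if the stop date is Day 8 (1 day too many), or 15 − 1 + 1 = 15 days if it is Day 1 (8 too many). The 1-to-2-day range therefore belongs to daily dosing only.

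**Corrected formula.** In the daily example, restart minus first missed day is 21 − 11 = 10. Starting from the last dose, 21 − 10 − 1 = 10. Both give exposure of 30 − 10 = 20, which is the true value. In the weekly example, restart minus first missed scheduled dose gives 7.

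**The case against.** The best defence is that the added day follows the Appendix A convention and that the result hardly matters. The first part explains the formula without justifying it: the general rule counts both end dates, and here the end date is a dosing day. The second part largely stands. The quantity is summarised descriptively, and Section 9 plans no inferential safety comparison unless otherwise specified.

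Several stronger readings are tempting but not supported.

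- *Safety rates are biased.* They are not. Section 9.2.4 uses time on study and does not subtract interruptions. Summed doses and compliance (tablet counts) do not use interruption length, and efficacy times do not use it either.
- *The comparison between arms is distorted.* An arm with more interruptions would lose more days, but the document gives no interruption rates by arm. Even several extra interruptions would move exposure by days over years.
- *Short holds will be reported at two or three times their length.* The formula does turn a one-day hold under daily dosing into 2 or 3 days. Section 9.1, however, says only that interruptions will be summarised. It does not say their length will be tabulated, and a count would be unaffected.
- *Every interruption is off by 1 to 2 days.* That is exact for daily dosing. On the modified regimens a count of days off drug is not defined until the stop date is.

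**Conclusion.** The formula is wrong as written, and nothing elsewhere in the SAP corrects it. Under daily dosing it understates exposure duration by exactly 1 day per interruption (stop date = first missed day) or 2 days (stop date = last dosed day). Under once- or twice-weekly dosing, measured from the first missed scheduled dose, the excess is at least 1 day and can be larger if the last dose is used as the stop date.

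This is a minor point. The percentages rest on assumed 7-day gaps, daily dosing and three interruptions per subject; more interruptions or shorter follow-up would raise them. No efficacy or safety conclusion depends on the quantity. It is worth correcting because the error is certain and the correction is cheap.

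**What to change.** In Section 9.1, define the date of temporary discontinuation as the date of the first scheduled dose not taken, and set the duration of each interruption to the restart date minus that date, with no added day. State that this overrides the general duration rule in Appendix A. Leave the rest of the exposure formula unchanged.

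If the case report form records only the last dose taken, derive the first missed scheduled dose from the subject's dosing regimen. For daily dosing this reduces to restart date − last dose date − 1. That shortcut should not be used on the weekly schedules: in the weekly example above it would give 15 − 1 − 1 = 13 days instead of 7.

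The cost is a sentence or two of SAP text and a small program change. Subjects on the modified schedules may also need the derivation from their dosing records. No new data have to be collected.

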4.2. Per Protocol (PP) Population

The PP Population includes ITT subjects who do not have any major protocol deviations that potentially affect the primary efficacy conclusion. Major protocol deviations that exclude subjects from the PP population are:

- Subject randomized into the study despite not meeting inclusion criteria or meeting exclusion criteria.
- Potential overdose, i.e. investigational product compliance $>120\%$, unless there's clear documentation.
- Subject met protocol criteria for down-titration, but dose was not adjusted.
- Prohibited change in concomitant medication whilst actively on the study, including commercial OCA.
- SAE not reported or not reported in required timeframe.
- Failure to submit local subject level safety events per IRB/EC policy.
- Withdraw criteria met, but subject not discontinued.

The PP Population will be used for the sensitivity analyses of the primary and key secondary efficacy endpoints. Treatment assignment will be based on the randomized treatment. PP patients list will be determined prior to unblinding.

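### Compliance as defined in SAP section 9.1 cannot exceed 100%, so the >120% per-protocol exclusion in section 4.2 cannot be met, and the ratio ignores the prescribed regimen

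*SAP*

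**What the plan says.** Section 9.1 introduces one compliance percentage: "Subject's overall compliance (%) with IP will be calculated as follows", namely 100 times tablets consumed over tablets expected. The denominator is "number of tablets expected to be consumed during study = number of dispensed tablets during the study". The numerator is "number of tablets consumed during study = number of tablets dispensed – number of tablets returned". The percentage is to be summarised separately for completers and early withdrawals, "so as to distinguish between those subjects who were compliant throughout the entirety of the study versus those who were compliant until they withdrew".

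Section 4.2 lists seven major deviations that exclude a subject from the PP population. One of them is "Potential overdose, i.e. investigational product compliance $>120\%$, unless there's clear documentation". The section adds that "The PP Population will be used for the sensitivity analyses of the primary and key secondary efficacy endpoints" and that the PP list is to be settled before unblinding.

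The dosing table in section 3 has daily, once-weekly and twice-weekly schedules with titration. Section 9.1 itself recognises modified frequency, interruptions and rechallenge. Neither the interim SAP nor the clinical pharmacology analysis plan in the same file offers another definition of compliance with investigational product.

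**The concern.** The two sections do not fit together. Section 4.2 needs a ratio that can go above 120%, while section 9.1 builds one in which the same count of dispensed tablets heads the numerator and forms the whole denominator. One of the seven pre-specified PP exclusions is then empty whatever the data show.

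The same definition raises a second problem. What a subject was told to take appears nowhere in the formula. The result is the share of dispensed tablets that did not come back. It equals adherence only if exactly the prescribed number is dispensed and every untaken tablet is returned.

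Two outputs are at stake: the composition of the PP population, and the meaning of the compliance table, including its stated aim of separating subjects who were adherent until withdrawal from those adherent throughout.

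**Working it through.** **Inputs.** D = tablets dispensed and R = tablets returned, with 0 ≤ R ≤ D (section 9.1). The threshold is 120% (section 4.2). The SAP gives no pack sizes or dispensing quantities, so every tablet count below is an assumption for illustration.

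**Step 1: the ceiling (no assumption needed).**

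Compliance = 100 x (D - R)/D = 100 x (1 - R/D).

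- Maximum, at R = 0: 100%.
- Minimum, at R = D: 0%.
- To exceed 120%: 1 - R/D > 1.20, so R/D < -0.20. That is a negative number of returned tablets.

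A check over all whole numbers D from 1 to 500 and R from 0 to D gave the same limits, 0.0% and 100.0%. The criterion selects no subject.

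**Step 2: how the ratio depends on surplus supply.** Let P be the tablets prescribed over the period. A fully adherent subject who returns everything unused scores 100 x P/D.

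| Prescribed P | Dispensed D | Section 9.1 compliance | Taken/prescribed |
|---|---|---|---|
| 90 (daily, 90 days) | 90 | 100% | 100% |
| 90 | 100 | 90% | 100% |
| 90 | 120 | 75% | 100% |
| 90 | 150 | 60% | 100% |
| 13 (weekly, about 90 days) | 13 | 100% | 100% |
| 13 | 30 | 43.3% | 100% |
| 13 | 100 | 13% | 100% |

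Only supply differs between rows with the same P; behaviour is identical.

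**Step 3: subjects who take more than prescribed.**

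| Prescribed | Dispensed | Taken | Section 9.1 compliance | Taken/prescribed |
|---|---|---|---|---|
| 90 | 120 | 120 | 100% | 133.3% |
| 90 | 150 | 120 | 80% | 133.3% |
| 13 | 30 | 16 | 53.3% | 123.1% |
| 13 | 30 | 26 | 86.7% | 200% |

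Each of these exceeds 120% of the prescription, and none exceeds 100% under section 9.1. Their section 9.1 scores, from 53.3% to 100%, overlap those of the fully adherent subjects in step 2.

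**Step 4: withdrawal and loss.** A subject adherent until withdrawal who hands back the remaining supply scores below 100%. One who withdraws and returns nothing scores 100%, because every unreturned tablet, including a lost one, counts as taken. The comparison of completers with early withdrawals therefore partly reflects who returned tablets.

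**The case against.** The strongest reply is that section 4.2 does not cross-refer to section 9.1. It sits in a list of protocol deviations, allows for documented exceptions, and could rest on a case review that uses a different calculation in the protocol or deviation log, neither of which is shown. This cannot be excluded. But the SAP points to no such calculation, ties overdose to a compliance percentage, and defines that percentage once. The reply limits the claim to the SAP's own definition and does not resolve the conflict.

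The second reply is about supply. If dispensing tracked the regimen exactly, perfect adherence would read 100%, and the distortion in step 2 would vanish for subjects who stay on schedule. That is correct. The weekly figures run from 100% down to 13% only because the assumed supply does. The 100% ceiling does not depend on supply.

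A reader might also infer more than the documents support:

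- That the PP analyses do retain subjects who overdosed. Nothing shows that any such subject exists; only that one would not be caught.
- That the compliance summary is wrong for the modified-dosing group. It can be, depending on an unstated surplus. Section 3 says most subjects dose once daily, and the SAP does not single out the modified group as the one where exposure matters most.
- That anyone taking too many tablets reads as 100% compliant. That occurs only when nothing is returned; otherwise the reading is lower, as step 3 shows.
- That exposure reporting fails as a whole. Section 9.1 separately summarises duration net of interruptions, total dose taken, dose changes and rechallenge.

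**Conclusion.** The point holds as a contradiction within the SAP. With compliance defined as in section 9.1, the >120% criterion in section 4.2 flags zero subjects by construction, and any subject above 120% of prescribed tablets would remain in the PP population. This part is exact and rests only on the number of returned tablets not being negative.

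The regimen-blind denominator is also established: the statistic is the unreturned share of dispensed tablets. How far it departs from adherence cannot be sized from the documents, because surplus supply and return rates are not given. The number of subjects affected is likewise unknown.

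The consequence is moderate. It reaches the PP sensitivity analyses of the primary endpoint (section 8.1.2) and of the key secondary endpoints (section 8.2.2), including the endpoint that section 8.2 makes primary for the EMA filing, together with a descriptive table. The primary analysis uses the ITT population (section 4.1) and does not change. The correction should be made, but the main conclusion does not turn on it.

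**What to change.** Before the PP list is fixed and before unblinding:

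1. In section 9.1, define expected tablets as the sum over dosing periods of (prescribed tablets per dosing day x scheduled dosing days), net of documented interruptions, following each subject's recorded regimen and titrations.
2. Keep consumed = dispensed - returned, and state how unreturned or lost tablets are handled.
3. In section 4.2, cross-refer the 120% criterion to this ratio. If a different calculation was intended for deviations, write that one down instead.

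Under this definition the threshold can be reached: 120 tablets taken against 90 prescribed gives 120/90 = 133.3%. It still requires more than 1.2 times the prescribed number to have been dispensed.

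The cost is a wording change in two sections and some programming. Section 9.1 already plans to summarise dose adjustments and interruptions, so the inputs should be on file. No dose or clinical rule changes.
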